CAB Members associated with each CHC will thereby facilitate the adaptation of the intervention strategies to the local culture and clinic culture, enabling LFLS to work with the community rather than imposing the program on the community.

No personal, individually identifying information will be collected and no individual interviews or assessments will be conducted with CAB Members.

Focus Group Discussion (FGD) Members. FGD members will meet in gender concordant groups in a private room within their experimental clinic site; members will provide input on cultural factors that influence attitudes, perceptions, and beliefs about EIMC among pregnant couples.

They will provide guidance on cultural attitudes, ethnic preferences, beliefs and perceptions surrounding EIMC among pregnant couples in Lusaka. FGD members will inform the study on local issues or community concerns that could influence program uptake. No personal, individually identifying information will be collected and no individual interviews or assessments will be conducted with FGD members.

Couples Assessments.

Assessments at baseline will be completed using audio computer-assisted self-interview (ACASI) software, with support from study staff as needed. Participants will be assessed individually in a private office in the CHC; ACASI headphones and touchscreen computers will provide confidentiality and privacy. LFLS session 2 will be scheduled to coincide with the post-partum neonatal clinic visit in the first week following birth.

Each assessment measure (see attachment) is related to the study theoretical model, outcomes (feasibility, acceptability, uptake) and associated factors (e.g., plans, knowledge, norms, attitudes/beliefs and cultural or religious values associated with EIMC/VMMC, family decision making, stage of readiness).

After each LFLS session, a brief paper-based questionnaire will be individually administered to assess Stage of Change. VMMC/EIMC uptake and the role of parents, family members, peers and HIV serostatus in decision-making will be assessed by telephone or office visit at 6 months post-partum.

Couples intervention.

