influential other, if desired. EIMC brochures will be distributed and Stages of Change questionnaires will be administered prior to the session

Topics: Why undergo EIMC? What are the benefits? Why now? When is the best time for EIMC? Information: What happens? How long does it take? Is it painful, how is pain controlled? What happens next? How long is healing, cleaning during healing? What happens to the foreskin? What are the risks? Is it safe? Who should be involved in the decision? Any additional questions or concerns about EIMC?

Session 2 will include the opportunity for couples to bring a person culturally connected to making the EIMC decision to the session (e.g., paternal mother) (Mavhu et al., 2017). To enhance acceptability, LFLS sessions will be developed from CHC CAB members, focus group discussions, and health care staff. Content will be pertinent to the critical cultural, social and religious issues and beliefs affecting EIMC decision making, and will consider research in Zambia on this topic (e.g., Waters et al., 2012; 2013). The two LFLS sessions will be manualized, based upon the community input, and “fine-tuned” using feasibility pilot data. The preliminary outline, from focus discussions in Zambia, is proposed below.

Topics: Any new questions or concerns about EIMC? How does EIMC differ from VMMC? What is the religious view on EIMC? What does my culture say about MC? What was the purpose of the foreskin? (How long is it needed?) Will EIMC affect future sexual performance, functioning & potency? Final questions? Stages of Change questionnaires are administered prior to the session.

Location. All research procedures will be performed at the clinic sites, in private offices and meeting rooms.

Risks.

There are no drugs or devices used in this study; all procedures discussed (EIMC, VMMC) are available for uptake at the clinics and are evidence based practices.

Procedures to lessen the probability or magnitude of risks.

Source records used to collect data. All surveys, scripts, and data collection forms are being developed during the formative period of this study.

Proposed Assessments at baseline (see attachment for initially selected assessments):

Instruments will be adapted from S&S1 and previous VMMC/EIMC studies (~45 minutes).

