1) Demographics, to include gender, age, marital status, male children MC status, education, income, father's MC status, HIV status (All public health facility users are required to undergo HIV testing per GRZ policy) (adapted, Kabwe, 2016 and [name] et al., 2015).

2) Stages of Change EIMC items (Precontemplation, Contemplation, Preparation, Action, Maintenance) will be adapted from Redding et al. (2015).

3) EIMC knowledge, norms, attitudes/beliefs items (adapted from [name] et al., 2010; Chilimampunga et al., 2017; Kabwe, 2015; Mugyawana et al., 2011; Waters et al., 2013; Young et al., 2016).

4) VMMC knowledge, norms, attitudes/beliefs items will be evaluated using an adaptation of Kebaabetswe et al. (2003), [name] et al. (2015)

5) EIMC/LFLS Intervention acceptability and feasibility at the clinic level will be assessed using an adaptation of Chilimampunga et al. (2017) and Mavhu et al. (2015). Topics include review of the

IRB Study Number:

Version #, Date:

S&S+LFLS model, and the incorporation of EIMC services in the clinic, advantages and/or disadvantages of the program, and changes or recommendations for the program. Staff and CAB members will participate in clinic meetings to evaluate feasibility and acceptability of the S&S+LFLS program.

- 6) EIMC decision making will be assessed using items adapted from the conceptual model developed by Mavhu et al. (2017).
- 7) EIMC/VMMC Individual level Uptake. EIMC outcome, male infant; VMMC outcome, fathers and sons in the household, sex of infant & birth status (M/F; Live/Lost). VMMC/EIMC uptake and the role of parents, family members, peers and HIV serostatus in the decision-making process will be assessed by telephone or private office visit at 6 months post-partum.
- 8) EIMC/VMMC Clinic level Uptake. CHCs will provide 12 months of historical VMMC/EIMC rate data prior to VMMC/EIMC and S&S+LFLS training. Clinics will also collect real-time comparative VMMC/EIMC monthly aggregate data for the duration of the study (Monthly EIMC/VMMC conducted following EIMC/VMMC training (M6) to M30). Historical period: Monthly CHC EIMC/VMMC conducted for 1 year prior to EIMC/VMMC training.

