Following baseline assessments, couples will complete a brief Stages of Change questionnaire prior to each prenatal and one-week post-partum LFLS sessions. Couples will be assessed at 6 months post-partum to evaluate EIMC and VMMC uptake by father, sons and infant to examine the interactive influence of EIMC and VMMC uptake, as well as the role of both parents, family members, peers and HIV serostatus in the decision-making process (Montaño et al., 2018; Mavhu et al. 2017; Cook et al., 2015; [name], Cook et al., 2014) (see Assessments).

13) Data and Specimen Banking* n/a

14) Data Management*

Analytic Plan and Power Analysis

Aim 1. Develop, pilot and conduct formative, process and outcome evaluations to assess the CHC level feasibility and acceptability of S&S+LFLS.

Aim 2. Assess the intrapersonal, interpersonal, structural, and sociocultural factors relevant to the LFLS intervention, and develop program components to respond to these factors.

Hypothesis 2. Father's circumcision status, paternal grandparents' circumcision attitudes, peer circumcision attitudes, father's HIV status, and mother's HIV status will be indirectly related to the decision to choose EIMC through the father's circumcision attitudes. A mother's circumcision attitudes will be influenced by her HIV status, and her protective attitudes toward the newborn which will also influence the father's circumcision attitudes.

Aim 3. Assess whether the combined S&S + LFLS pilot program will increase uptake of EIMC at clinic level.

Hypothesis 3. The S&S + LFLS experimental condition clinics will have significantly higher numbers of EIMC in comparison with observation condition clinics.

Hypothesis testing. The analyses for this feasibility pilot study will begin with examination of frequencies, means, skewness, and kurtosis across study variables (EIMC, VMMC, HIV status, attitudes) to assess normality. We will conduct 1) analysis of qualitative data, 2) a path model to explore undergirding sociocontextual factors of a father's decision to elect EIMC or VMMC for his male children, 3) a test of comparison between conditions.

IRB Study Number:

Version #, Date:

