Exploratory analyses. To investigate change in EIMC attitudes, Stages of Change scores will be examined over time using an autoregressive modeling approach specifying the individual's stage at 1-week postpartum as the main outcome and individual's stage at baseline as a main predictor in the regression model (Hamaker et al., 2015). Variables from the previous path model will be included as potential covariates in attempting to explain stage movement. The estimated regression coefficient will reflect changes in EIMC attitudes over time. The model will use an ordinal logistic model to examine change over time. Odd ratios will be estimated as a measure of effect size (Chen et al., 2010).

Power. Using a two-tailed Z test to test the difference in proportions between two conditions at an α level of .05, this study has over 80% power to detect a difference of 6.0% in EIMC rate between the two conditions. This difference in proportion translates to an effect size of an odds ratio (OR) = 2.4, which is considered a small (OR = 1.68) to medium (OD = 3.47) effect size, according to Chen et al. (2010). This 2.4 OR is based on an effect size found in previous research examining circumcisions ([name] et al., 2015). With these specified parameters, 80% power is achieved with 140 couples (out of ~151 couples with male infants).

Data Security. CAB and FGD participants will not provide any uniquely identifying information during participation in group discussion sessions. Pregnant couple participants in the intervention will be assigned a unique code upon entering the study. This number will identify all participant files, which will include no identifiable information. Access to the computer data files will be restricted by password codes. The list translating participant number to identifying information

IRB Study Number:

Version #, Date:

will be maintained in a secure locked file in the Spear & Shield study office in Lusaka at the University of Zambia School of Medicine. Participants will be made explicitly aware at the time of the informed consent of the nature of the separate record that will be kept for them. CAB and focus group discussions will be audio-taped for review and summary of key discussion points; copies will be stored in a locked cabinet at the PI's Lusaka offices, and deleted following summarization.

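### Stage of Change is taken by computer self-interview at baseline but on paper at the LFLS sessions, with no stated route for missed sessions, so apparent stage movement mixes change with mode and attendance

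*Combined protocol and SAP*

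**What the plan says.** - **Baseline mode.** Section 12, Couples Assessments: "Assessments at baseline will be completed using audio computer-assisted self-interview (ACASI) software, with support from study staff as needed". The same paragraph gives privacy as the reason for headphones and touchscreens.
- **Stage is in the baseline battery.** Item 2 of the proposed baseline assessments in Section 12 is "Stages of Change EIMC items (Precontemplation, Contemplation, Preparation, Action, Maintenance".
- **Later mode.** Section 12, Couples Assessments, says of the time following each session that "a brief paper-based questionnaire will be individually administered to assess Stage of Change".
- **Timing of the later form.** The description of LFLS Session 2 says "Stages of Change questionnaires are administered prior to the session", and Session 1 is described likewise. The paragraph that closes Section 12 says "couples will complete a brief Stages of Change questionnaire prior to each prenatal and one-week post-partum LFLS sessions".
- **Missed sessions.** No route is given for the stage form. The 6-month uptake assessment, by contrast, may be done by telephone or office visit.
- **Analysis.** Section 14, Exploratory analyses: "Stages of Change scores will be examined over time", using an ordinal logistic autoregressive model. Stage at 1 week postpartum is the outcome, baseline stage is the main predictor, and variables from the path model are possible covariates. The plan reads the coefficient as change in attitudes.
- **Missing data.** Full information maximum likelihood is named under H2 and not repeated for the stage model.
- **Comparison.** Section 12, Design: observation clinics recruit no participants and supply aggregate counts only.

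**The concern.** Every respondent changes survey mode at the step from baseline to the first follow-up form. If people answer differently on paper, at a session that promotes EIMC, than on a touchscreen, that difference appears as stage movement. With no comparison group for stage, the data cannot separate the two.

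The follow-up form is also tied to a session. Session 2 is a 90-minute couples session in the first week after birth, so some absences are foreseeable, and Section 16 lets bereaved couples leave or defer. If less receptive couples are likelier to stay away, those who are measured will look readier than those who enrolled.

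The Background gives some reason for care about stated readiness. In a cited study of Zambian pregnant women, 97% said that they would circumcise a son and 11% did so. This does not prove a mode effect, but it shows that expressed willingness can exceed behaviour. At stake is how far stage movement in this pilot can inform the later trial that Section 12 mentions.

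**Working it through.** The documents give no sample size, power or expected effect for the stage analysis, so there is no figure of the plan's to reproduce. The check has three parts.

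**1. The measurement occasions side by side**

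| Occasion | Mode | Collected from |
|---|---|---|
| Baseline | ACASI | all enrolled partners |
| LFLS Session 1 (prenatal) | paper | those at the session; no other route stated |
| LFLS Session 2 (first week postpartum) | paper | those at the session; no other route stated |

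Mode and time coincide from baseline to either paper form. They do not coincide between the two paper forms, which are a same-mode pair. If the forms come before the sessions, that pair spans Session 1; if after, it spans Session 2. The planned model, however, uses baseline stage as its main predictor.

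**2. Selective attendance, simple arithmetic (all inputs assumed)**

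Let readiness be 60% in attenders and 30% in others.

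Overstatement = (1 − attendance) × (60% − 30%)

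- Attendance 90%: 0.10 × 30 = 3 points.
- Attendance 70%: 0.30 × 30 = 9 points.

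This is bias in the raw proportion ready, not in a model that conditions on baseline stage.

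**3. Illustration with no true change (all inputs assumed)**

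- Latent readiness at baseline is U + e0 and at follow-up U + e1 + m, with U normal (SD 1.5), e0 and e1 standard logistic, and m the uniform mode shift.
- Cut-points are set so that the five baseline stages hold 40, 25, 20, 10 and 5%.
- The mode odds ratio is exp(m), with m = 0, 0.4 and 0.7.
- The probability of attending is 1/(1 + exp(−(1 + g × follow-up latent value))), with g = 0.3 or 0.6; with no selection everyone is measured. The follow-up value includes m, so attendance rises slightly with m.
- Net advancement is the share moving up minus the share moving down, among those measured.
- The last column is the odds ratio per baseline stage from an ordinal logistic fit of follow-up stage on baseline stage (40,000 simulated respondents before attendance).

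| Mode OR | g | Attendance | Net advancement (points) | OR per baseline stage |
|---|---|---|---|---|
| 1.00 | none | 100% | −0.3 | 1.83 |
| 1.00 | 0.3 | 71% | +5.7 | 1.78 |
| 1.00 | 0.6 | 67% | +10.9 | 1.71 |
| 1.49 | none | 100% | +10.5 | 1.83 |
| 1.49 | 0.3 | 73% | +16.5 | 1.79 |
| 1.49 | 0.6 | 71% | +21.5 | 1.71 |
| 2.01 | none | 100% | +18.7 | 1.84 |
| 2.01 | 0.3 | 75% | +24.5 | 1.80 |
| 2.01 | 0.6 | 74% | +29.0 | 1.73 |

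Mode and attendance each create apparent movement where there is none. The fitted coefficient behaves differently. A uniform mode shift leaves it at 1.83 to 1.84, because the shift goes into the thresholds: with everyone measured, the first threshold falls from 0.24 to −0.07 to −0.30. With no mode shift, selective attendance lowers the coefficient from 1.83 to between 1.71 and 1.78.

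**The case against.** **Readings that the documents do not support.** A reader might infer that the later forms are administered by staff in a less private setting. The text says only that they are individually administered, which allows self-completion. Staff may also support the ACASI, and the Potential Risks section places assessments in a private office. The mode change stands; a sharp privacy contrast does not.

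A reader might also infer that only attenders can have a 1-week stage. That comes from silence. Every couple is meant to attend, and Section 10 lists the postpartum assessments separately from the sessions. Session 2 is timed to the neonatal clinic visit, visits are compensated, and Section 24 allows special follow-up efforts. These reduce the likely loss, but none says how the stage form is obtained after a missed session.

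**The analysis.** A reader might expect a mode artefact to produce a false significant result. Suppose that 15% move up and 10% down: z = 0.05n/√(0.25n × design effect) = 0.1√(n/design effect). With n = 600 and no design effect, z = 2.45. But no such test is planned, and 600 leaves no room for absence. At 70% attendance (n = 420) and an assumed design effect of 1.5, z = 1.67. With only the roughly 151 couples with male infants (n = 302), z = 1.74 before any design effect. The planned coefficient is hardly moved by a uniform shift. That objection stands. It does not rescue the stated interpretation, because the coefficient measures how stable stage is, not how much it changed.

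**Importance.** The analysis is labelled exploratory. The programme-effect test is H3, on EIMC, and the primary endpoints are EIMC and VMMC uptake. All of this stands.

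**Missing-data method.** If full information maximum likelihood is meant to cover this model too, it helps only if missingness is at random given the modelled variables. It would not remove selection on receptiveness that those variables do not capture.

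**Conclusion.** The point holds in a limited form. The amount of stage movement from baseline to 1 week postpartum is mixed with a change of survey mode. The 1-week outcome may be missing selectively for partners who miss Session 2. There is no comparison group for stage with which to separate these from real change. Attendance is a selection problem rather than confounding.

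The size cannot be known from the documents. The 6 to 29 points of apparent net advancement across the rows with a mode shift, selective attendance or both are illustrations that rest on the assumed mode effects, attendance and stage distribution. They are not estimates for this trial. A reader might infer that the artefact would be taken for a programme effect or reach the trial's main conclusions. The documents do not support that: the plan interprets this analysis as change over time, and the uptake endpoints do not use it.

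The before-or-after contradiction is a separate documentary fault in the same procedure. It decides whether the 1-week stage can include any effect of Session 2. This is an inexpensive improvement to an exploratory analysis, not a threat to the main results.

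**What to change.** 1. **One mode.** Give the stage items in the same mode at baseline and both sessions: ACASI at the sessions, or the same brief paper form added at baseline.
2. **A route for missed sessions.** For partners who miss Session 2, collect the same items in the same week at the neonatal visit or, failing that, by telephone. Couples who lose a baby remain under the Section 16 arrangement.
3. **Analysis.** Keep all enrolled partners in the stage analysis, state the missing-data method for this model, and add a sensitivity analysis for missing or telephone-collected outcomes. Record the mode, but do not rely on a mode flag alone, since it would be confounded with non-attendance.
4. **Timing.** Reconcile the Couples Assessments paragraph with the LFLS session descriptions and the closing paragraph of Section 12, so that one statement says whether the form comes before or after the session.

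**Cost.** A few minutes per session and brief calls to missed partners: at an assumed 70 to 90% attendance, 300 × 0.30 = 90 down to 300 × 0.10 = 30 couples. A small mixed-mode subgroup would remain. The Project Offices paragraph before Section 25 lists 12 laptops for ACASI, but does not show that they would be free at the four clinics. If they are not, the paper form at baseline avoids the question.

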H2. Assess factors relevant to the LFLS model. To investigate the indirect effects of the five main predictors (paternal grandparents' circumcision attitudes, peer attitudes surrounding circumcision, father's HIV status, father's circumcision status, and mother's HIV status) on infant circumcision, a path analysis (Kline, 2011) will be conducted. To estimate the indirect effects, it will be specified that the paths between the five main predictors on infant circumcision will act through father's circumcision attitudes. Mother's circumcision attitudes will be regressed on mother's HIV status, and a regression path between father's and mother's attitudes toward circumcision will be specified. When estimating the indirect effects, results will be adjusted for the effect of number of siblings circumcised.

All potential indirect effects will be estimated by a bootstrapping approach (MacKinnon et al., 2007). R-square of indirect effects will be used as measures of effect size (Fairchild et al., 2009). A sandwich estimator will be used to account for the nested data structure (e.g., individuals are nested by clinics). This estimator uses the Huber/White correction and adjusts for potential underestimated standard errors and bias in chi-square computation (Liang & Zeger 1986).

Missing data will be handled using Full Information Maximum Likelihood estimation procedures (Enders & Bandalos 2001). For model fit evaluations, we will use well-established fit indices and cutoff values: A well-fitting model ideally will have a non-significant model χ^2 , a Comparative Fit Index / Tucker-Lewis Index greater than .95, a root mean square error of approximation less than .08, and a standardized root mean square residual less than .08 (Hooper et al., 2008). All analyses will be conducted in Mplus (V8; Muthén & Muthén, 2017).

H3. Effect of S&S + LFLS pilot. To compare the proportion of EIMCs in the experimental group to the proportion found in the observation group, a one-sample z-test will be conducted. The population proportion will be taken to be the midpoint of the findings from Waters et al. (2013) on neonatal circumcision and historical numbers of circumcisions from Zambian clinics and hospitals. Based upon this rationale, the percentage of EIMCs in the observation group is anticipated to be approximately 5.0%.

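### H2 combines R-square, FIML and covariance-fit cut-offs for a yes/no outcome; they fit together only if the event is treated as continuous, and R-square then depends on how rare it is

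*Combined protocol and SAP*

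**What the plan says.** The outcome is defined in Section 12, Proposed Assessments, item 7, as "EIMC outcome, male infant": one yes/no result per boy. Section 14, under H2, makes it the end point of a path analysis. Five predictors act through the father's circumcision attitudes, and the mother's attitudes also feed into the father's. Indirect effects are bootstrapped and adjusted for the number of circumcised siblings.

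For this one model the plan then sets four further rules:

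- Effect size: "R-square of indirect effects will be used as measures of effect size".
- Missing data: "Missing data will be handled using Full Information Maximum Likelihood estimation procedures".
- Clustering: "A sandwich estimator will be used to account for the nested data structure".
- Fit: "A well-fitting model ideally will have a non-significant model". That wording refers to the chi-square test; the other targets are CFI and TLI above 0.95, with RMSEA and SRMR each below 0.08.

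The plan does not say whether infant circumcision enters as a continuous or a categorical variable, and no logit, probit or threshold model is named. The Hypothesis testing paragraph includes EIMC among the variables to be screened for normality. By contrast, the Exploratory analyses paragraph names an ordinal logistic model with odds ratios for Stages of Change.

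**The concern.** Variance-explained R-square for mediation and the listed fit indices come from linear models for continuous variables. Applied to an uncommon 0/1 event, R-square depends on the event rate and on how each predictor is distributed, as well as on the strength of mediation. If the analyst instead treats the event as categorical, one of the stated rules has to be dropped or replaced, and the plan does not say which.

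Aim 2 is to assess these factors and to develop programme components that respond to them, and the pilot is meant to prepare a later trial. An indirect effect whose reported size reflects rarity and predictor prevalence is a poor guide for that, and it does not carry over to a sample with different uptake. With few events expected, the model and the reporting scale should be fixed before the data are seen.

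**Working it through.** **Inputs from the documents.** The reference EIMC rate is 5.0% (Section 14, H3). The detectable difference is 6.0 percentage points, with 140 couples needed out of about 151 with male infants (Section 14, Power). Participants are enrolled at the four experimental clinics only (Sections 7 and 12). H2 has no stated sample size, power or effect size, so the H3 figures are used only to obtain a rate and a number of boys.

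**The plan's own figure first.** The implied experimental rate is 5.0% + 6.0% = 11.0%. The odds ratio is (0.11/0.89)/(0.05/0.95) = 2.35, against 2.4 stated. For the one-sample z-test named under H3, two-sided 0.05, n = 140:

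[0.06 − 1.96·√(0.05·0.95/140)] / √(0.11·0.89/140) = 0.904, so power = 81.7%.

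This agrees with the stated 80%, so 5% and 11% are the rates behind the plan.

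**Expected events.** 151 × 0.11 = 16.6, and 151 × 0.05 = 7.6.

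**Reading A: the event is fitted as continuous.** FIML and every listed index are then available. Assume a normal latent propensity and small effects. The ratio of R-square on the 0/1 outcome to R-square on the latent scale is φ(z_p)² / [p(1 − p)]:

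| Uptake p | φ(z_p)² | p(1 − p) | Ratio |
|---|---|---|---|
| 5% | 0.0106 | 0.0475 | 0.22 |
| 11% | 0.0354 | 0.0979 | 0.36 |
| 50% | 0.1592 | 0.2500 | 0.64 |

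**Is the compression the same for every predictor?** Use the R-square of the indirect effect, r²_YM − (R²_Y.MX − r²_YX), in a simulated chain X → M → Y*. All variables are standardised, the paths are 0.4 and 0.5, X is binary, and n = 2,000,000. These settings are assumptions; the documents give none. The latent-scale value is 0.040 whatever the prevalence of X. At 11% uptake:

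- X present in 22%: 0.019, a retained share of about 0.47.
- X present in 50%: 0.014, about 0.36.
- X present in 78%: 0.0097, about 0.24.

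A promoting factor present in 78% is the same thing as a deterrent present in 22%. So a promoter and a deterrent that are equally common and equally strong would be reported with R-squares differing about twofold.

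A fuller simulation of the H2 model, again with assumed coefficients, gave at 11% uptake 0.010 against 0.027 on the latent scale for grandparent attitudes, and 0.006 against 0.013 for the father's circumcision status. Retained shares were 0.35 to 0.44 at 11% and 0.22 to 0.29 at 5%.

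**Can the fit cut-offs be met under Reading A?** In 2,000 simulated samples of 151 with a correctly specified model (12 degrees of freedom, no missing data, no clustering), all cut-offs were met together in about 62% of samples at 11% uptake and 60% at 5%, against 73% when the outcome was truly continuous.

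**Reading B: the event is declared categorical.** A full-information logit or probit likelihood is not a fit to a sample covariance matrix, so it yields no covariance-structure chi-square from which CFI, TLI, RMSEA and SRMR could be computed. A limited-information categorical estimator yields such indices but is not FIML. The R-square compression of Reading A does not arise on the latent-response scale.

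**The case against.** The strongest reply is that this is an exploratory path model in a feasibility pilot and that the two difficulties belong to different readings, so they never occur together. That is correct. A reader might infer that the effect sizes are understated and also that the stated rules cannot all be met. The documents do not support that combination: under a continuous fit the rules can all be applied and were often met in simulation, and under a categorical fit the compression is absent. The cut-offs are also worded as an ideal, not as pass/fail rules.

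Further points stand:

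- Compression is measured against a latent scale that the plan does not define. A low R-square on the observed event is a matter of scale, not bias against a declared target.
- The 5% is the reference rate, whereas H2 uses experimental clinics only. The 11% is implied by the detectable difference and is not a forecast.
- The simulated shares rest on assumed paths and prevalences.
- A reader might infer that Aim 2 ranks factors by R-square. The documents do not say so, and intervention content also comes from advisory boards, focus groups and staff. In the fuller simulation the order of the paths did not change.
- Probability differences also depend on the base rate: an odds ratio of 2.4 is about +6 points from 5% but +17.5 points from 20%.

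What the reply does not answer is that the written rules are coherent only under the continuous fit, and that this fit makes the chosen effect size depend on event rate and predictor prevalence. The exploratory purpose lowers the stakes, but a better method is available at little cost.

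**Conclusion.** The concern holds in this form: the H2 rules are mutually consistent only if a yes/no outcome is fitted as continuous. R-square is then compressed to about 0.36 of a normal latent-scale value at 11% uptake and 0.22 at 5%. At 11% the retained share varied from about 0.24 to 0.47 over predictor prevalences of 78% to 22%, so mediated effects of equal strength can look unequal. If the outcome is categorical, FIML and the listed fit indices do not go together.

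The 0.36 and 0.22 factors depend only on the event rate, a normal latent variable and small effects; the 0.24 to 0.47 range also depends on the assumed paths. The documents do not support saying that the effect sizes are wrong in absolute terms, that no fit could satisfy the plan, or that a decision would be reversed.

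**What to change.** In Section 14, H2:

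1. Declare infant circumcision binary and fit it with a logit or probit link by maximum likelihood, which keeps full-information handling of missing data.
2. Replace R-square by each indirect effect expressed as a difference in EIMC probability (or as an odds ratio), with the bootstrap interval already planned, and state the base rate at which it is evaluated.
3. Apply the chi-square, CFI/TLI, RMSEA and SRMR cut-offs only to the equations for the mother's and father's attitudes.

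The change is to the analysis text only; no data collection alters. The cost is the loss of a single overall fit index. Testing the omitted direct paths does not fully replace it: five direct paths added to father's attitudes and siblings circumcised make seven coefficients, or 16.6/7 = 2.4 events each at 11% uptake (7.6/7 = 1.1 at 5%). Any such check should be labelled descriptive.
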